9.3 Data Analysis Plans

Data will be analyzed after enrollment and tumor assessments of the first 10 subjects to determine whether early stopping point has been met.

Analysis of Endpoints

- **9.3.1** Exploratory Data Analysis: Exploratory analyses will be performed to elucidate the relationships among variables. Graphical data analysis will be applied to examine the distribution of the data and to reveal the association among covariates and outcome variables. Statistical graphics provide effective data summaries and can be very useful for error checking and outlier identification. Standard distribution plots such as histograms and box-plots will be applied. A scatter plot matrix will be used to explore the association among multiple variables. The main purpose of the exploratory data analysis is to "let the data speak". These analyses not only provide an assumption free, graphical, presentation of the data, but can also be used to help select appropriate statistical models to use during data analysis.
- **9.3.2** Analysis of Survival Data: We will estimate the survival distributions for time-to-event outcomes using the method of Kaplan and Meier and compare these distributions among groups using the logrank test. Multivariable proportional hazards regression models will be used to assess which biomarkers are predictive of patient outcomes in the presence of covariates. The proportional hazards assumption will be evaluated graphically and analytically, and regression diagnostics (e.g., martingale and Shoenfeld residuals) will be examined to ensure that the models are appropriate. Violations of the proportional hazards assumption will be addressed by use of time-dependent covariates or extended Cox models. The possibility of collinearity will be reduced through the careful initial assessment of correlations among all study covariates.
- **9.3.3** Analysis of Categorical Response Variables: We will test for differences among groups using Pearson's chi-square statistic, or Fisher's exact test. In those situations where we must stratify on a characteristic of the population under study, we may employ the Cochran-Mantel-Haenszel test. In those situations in which we are interested in modeling the relationship between a binary response variable and single or multiple covariates, we will use logistic regression. Logistic regression diagnostics will be employed to ensure that the logistic model is appropriate. Similarly, the possibility of collinearity will be reduced through the careful initial assessment of correlations among all study covariates.
- 9.3.4 Analysis of Continuous Response Variables: For the analysis of continuous response variables, we will use analysis of variance (ANOVA), analysis of covariance (ANCOVA), and mixed models. We will test the data to ensure that the underlying assumptions (i.e., normality, homoscedasticity) of the ANOVA model are met. If these assumptions are not met, then we will attempt to transform the data such that the transformed data meet these assumptions. Standard transformations of the response variable such as the log, square root and Box-Cox transformations will be examined. If data transformation is inadequate to meet the analysis assumptions, then rank transformation of the data will be performed and one-way ANOVA on the rank transformed response variables will be analyzed and reported. In those situations where covariates could potentially have an effect on the response variable in an ANOVA context, we will use ANCOVA to adjust treatment effects. The underlying assumptions of the ANCOVA model will be tested (such as homogeneity of slopes across groups). Standard regression criteria will be used to assess appropriateness of including particular covariates. In situations where more than one covariate is being included in the model, the possibility of collinearity will be reduced through the careful initial assessment of correlations among all study covariates.
- **9.3.5** Analysis of Biomarker Data: Associations between biomarkers will be assessed using Cohen's Kappa with appropriate 95 percent confidence intervals reported. Kappas of .75 or greater are considered excellent, whereas Kappas between .4 and .75 denote good agreement.

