4.0 TREATMENT PLAN

4.1 Treatment Dosage and Administration

This is an open-label, single-arm pilot study in 20 subjects with advanced BRCA mutation or HDR-defect associated breast cancer having progressed through standard first line therapy.

The study participation is up to 35 administrations of pembrolizumab (approximately two years).

Pembrolizumab and olaparib will be supplied by Merck.

Pembrolizumab will be administered at a dose of 200mg as a 30 minute IV infusion Q3W. Effort should be made to target infusion timing to be as close to 30 minutes as possible. However, given the variability of infusion pumps, a window of -5 minutes and +10 minutes is permitted (i.e., infusion time is 30 minutes: -5 min/+10 min).

Olaparib 300mg will be self-administered orally twice daily. The dose of olaparib used in this study is 300 mg twice daily which is the currently approved dose. Subjects will complete a compliance diary throughout the study treatment period. Olaparib tablets should be taken at the same time each day, approximately 12 hours apart with one glass of water. The tablets should be swallowed whole and not chewed, crushed, dissolved or divided. Olaparib tablets can be taken with or without food. Each container will be labelled in accordance with Good Manufacturing Practice (GMP) Annex 13 and per country regulatory requirement. If vomiting occurs shortly after the olaparib tablets are swallowed, the dose should only be replaced if all of the intact tablets can be seen and counted. Should any patient enrolled on the study miss a scheduled dose for whatever reason (e.g., as a result of forgetting to take the tablets or vomiting), the patient will be allowed to take the scheduled dose up to a maximum of 2 hours after that scheduled dose time. If greater than 2 hours after the scheduled dose time, the missed dose is not to be taken and the patient should take their allotted dose at the next scheduled time.

The Pharmacy Manual contains specific instructions for pembrolizumab dose calculation, reconstitution, preparation of the infusion fluid, and administration.

Table 2. Trial Intervention

Drug Dose/Potency	Dose/	Route of	Regimen/ Treatment
-------------------	-------	----------	--------------------

		Frequency	Administration	Period
Pembrolizumab	200 mg	Q3W	IV infusion	Day 1 of each cycle
Olaparib	300mg	BID	PO	Continuous; dispensed
				each cycle day 1 (each
				cycle=3 weeks)

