9.2 Sample Size and Early Stopping

Clinical benefit is defined as complete response, partial response, or stable disease (if stable disease, lasting for at least four months). A proportion of patients with clinical benefit less than 15% will be of no interest. The new treatment would be of interest if the proportion of patients with clinical benefit is at least 41%. Simon's two-stage design (Simon, 1989) will be used. The null hypothesis: p<= 0.15 is against the alternative hypothesis p>= 0.41. In the first stage, 10 patients will be accrued. If there are 2 or fewer subjects with clinical benefit among these 10 patients, the study will be terminated. The probability of early stopping under the null is 0.82, and under the alternative is 0.16. Otherwise, 10 additional patients will be accrued for a total of 20. The null hypothesis will be rejected if 6 or more responses are observed in 20 patients. This design yields a 1-sided type I error rate of 5% and power of 80%.

The early stopping rule is based on responses in the first 10 patients, rather than dose limiting toxicity, as the study drug is FDA-approved at the current dose used in this trial, has a known and predictable rate of toxicity at the present dose, has been used in prior cohorts of breast cancer patients at the current dose, and there is no biological basis on which to expect excessive or unusual toxicity in the study cohort.

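### Section 9.3.2 plans multivariable Cox models to identify predictive biomarkers in a single arm of at most 20 patients; one-marker exact or penalised analyses, labelled as association, would be sounder

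*Combined protocol and SAP*

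**What the plan says.** Section 4.1 describes the trial: "This is an open-label, single-arm pilot study in 20 subjects". Section 9.2 lets it stop at 10 patients.

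Section 9.3.2 is firm about the survival models: "Multivariable proportional hazards regression models will be used to assess which biomarkers are predictive of patient outcomes in the presence of covariates". If hazards are not proportional, it adds time-dependent covariates or extended Cox models. Section 9.3.3 is conditional: where there is interest in "modeling the relationship between a binary response variable and single or multiple covariates, we will use logistic regression".

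The only biomarkers named are PD-1 and PD-L1 (Sections 2.3.1 and 8.0), under the exploratory and correlative objectives. The plan does not say how many covariates a model may hold, which ones are candidates, how coefficients are estimated when data are sparse, or how multiple tests are handled. The safeguards it names are residual diagnostics, proportional-hazards checks and a review of correlations among covariates. Section 9.3.1 also lets exploratory graphics guide the choice of model.

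**The concern.** There are two problems.

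- **Too little data per parameter.** At the 41% clinical-benefit rate of Section 9.2, 20 patients yield about 8 events (20 × 0.41 = 8.2). At the rejection boundary they yield 6. Large-sample likelihood tests reject too often in such data, and logistic fits can separate, giving an infinite odds ratio. Residual and collinearity checks do not cure this. The time-dependent extensions add parameters to the same data.
- **The word *predictive*.** In oncology it usually means that a marker identifies who benefits from the treatment. With no comparator, the design cannot show that.

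At stake is the reading of the PD-1/PD-L1 results, whose measurement is the main aim of the translational component. A chance finding could be carried forward under a label the trial cannot support.

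**Working it through.** **Inputs from the documents.** N = 20, or 10 after an early stop (Sections 4.1 and 9.2). Prevalence of PD-L1 is 21/30 = 70% and of PD-1 is 11/30 = 37% (Section 1.1). Binary event rates are 41%, the clinical-benefit alternative, and 6/20 = 30%, the rejection boundary (Section 9.2). Neither is a planning value for response rate; the documents give none.

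**Assumptions.** One, two, three or five binary covariates per model. The first two are PD-L1 and PD-1; the others are independent with prevalence 0.5, 0.5 and 0.4. Cox runs use 5 to 18 events. No covariate has any true effect.

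**1. The plan's own figures.** They exist only for the two-stage design. The stopping probability is P(X ≤ 2) with X ~ Bin(10, p): 0.820 at p = 0.15 and 0.152 at p = 0.41 (stated 0.82 and 0.16). The rejection probability, Σ P(X₁ = x)·P(X₂ ≥ 6 − x) over x = 3 to 10, is 0.0498 and 0.806, against the stated 5% and 80%. The plan gives no figure for the biomarker models.

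**2. Size of the nominal 5% likelihood-ratio test for one null marker, n = 20 (simulation).**

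| Covariates in model | Cox, about 12–16 events | Logistic | Logistic separation at 41% / 30% |
|---|---|---|---|
| 1 | 6–7% | 7–9% | 9% / 18% |
| 2 (PD-L1 and PD-1) | about 7–8% | about 8% | 13% / 26% |
| 3 | 9–11% (3 to 5) | 9–15% (3 to 5) | 19% / 32% |
| 5 | as above | as above | 30% / 47% |

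A second set of runs put separation with three to five covariates at 18–49%. Fisher's exact test on one marker stays below 3%.

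**3. Hand check of separation with PD-L1 alone.** The fit separates if any cell of the 2×2 table is empty. At 41%, the marker-negative cells have probabilities 0.3 × 0.41 = 0.123 and 0.3 × 0.59 = 0.177, and the marker-positive event cell 0.7 × 0.41 = 0.287. So the chance is about 0.877²⁰ + 0.823²⁰ + 0.713²⁰ = 0.072 + 0.020 + 0.001 = 0.09. At 30% it is 0.91²⁰ + 2 × 0.79²⁰ = 0.152 + 0.018 = 0.17. Both agree with the table. Even a single-marker model therefore needs an exact or penalised method.

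**4. At least one false positive among the Cox coefficients (Wald p < 0.05, 12 or more events).** It is 10–14% with two covariates, 18–19% with three and 30–32% with five. Exact, independent 5% tests would give 1 − 0.95ᵏ = 9.8%, 14.3% and 22.6%. Most of the total is ordinary multiplicity; the rest is small-sample inflation (7–9% per coefficient with three to five covariates).

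**5. Few events.** Non-estimable Cox fits, over one to five covariates, are 0–4% with 12 or more events, 10–23% with 8, and 26–64% with 5. With 10 patients and 8 events they are 12–61%. At 5 events the chance of any Wald rejection is only 1–6%, so the fault there is failure to fit. Overall survival is the exposed endpoint: patients who stop for progression leave follow-up at the 30-day visit (Section 5.15, footnote 4), so few deaths will be seen.

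**6. Single arm.** Write the log hazard as b₁M + b₂T + b₃MT, with marker M and treatment T. With T = 1 for everyone, the coefficient of M is b₁ + b₃. The prognostic part (b₁) and the predictive part (b₃) cannot be separated.

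**7. What one marker at a time can do.** A single-marker Cox model has a false-positive rate of about 5–7% and 0–3% non-estimable fits with 12 or more events. The hazard ratio detectable with 80% power (two-sided 5%, 50:50 split) is exp[(1.960 + 0.842)/√(0.25·D)] = 3.5 with D = 20 events and 5.0 with D = 12. With a 30:70 split it is 3.9 and 5.8. Two markers on response, clinical benefit, PFS and OS make eight tests; if independent, the family-wise error is 1 − 0.95⁸ = 34%.

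**The case against.** The other side has good arguments, and several narrow the point.

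- **Treatment benefit.** A reader might infer that the plan claims to show who benefits from the combination. It does not. Section 9.3.2 speaks of prediction of patient outcomes, which can mean plain association. This is loose wording, though Section 1.1 suggests that PD-L1 may predict responsiveness to pembrolizumab, so the looser reading is easy to fall into.
- **Logistic models.** A reader might infer that multivariable logistic models are committed to for finding biomarkers. Section 9.3.3 is conditional, permits a single covariate and names no biomarker. Only the Cox sentence makes that link.
- **Spurious or undefined results throughout.** The figures do not support this. With the two named markers the test size is about 7–8%, little above that for one marker. The higher figures need three to five covariates, which is an assumption. PFS Cox fits rarely fail with 12 or more events. The typical spurious hazard ratio of about 1.9 with five covariates mostly reflects sample size, since a single null marker already gives 1.5–1.7.
- **Importance.** The objective is exploratory, and no stopping rule or primary conclusion depends on it.
- **Existing tools.** Fisher's exact test, the log-rank test and single-covariate logistic regression are already in Section 9.3.

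These arguments limit the consequences to interpretation. They leave the firm commitment to multivariable Cox models, and the absence of any covariate limit or sparse-data method. That better-suited tests are already listed makes the correction easy. A bare switch to one-marker tests would leave multiplicity open, so the fix must address it.

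**Conclusion.** The point holds as a modest improvement to an exploratory analysis. The stated models are poorly matched to 20 patients. The excess over a nominal 5% is about 2–3 percentage points with the two named markers. It is about 4–6 points (Cox) or 4–10 points (logistic) with three to five covariates, together with frequent separation in the logistic fits. For Cox models, non-estimability matters chiefly for overall survival or after an early stop. The figures rest on the assumed number, independence and prevalence of the further covariates; the plan's silence on these is part of the fault. They also carry simulation error: 300 replicates, as in the Cox runs by number of events, give a standard error of √(0.05 × 0.95/300) = 1.3 points at 5%.

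That one arm cannot separate prediction from prognosis needs no numerical assumption. The documents make no claim of treatment benefit, so the remedy there is a change of word.

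**What to change.** For the exploratory PD-1/PD-L1 analyses in Sections 9.3.2 and 9.3.3:

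1. Replace the multivariable models with analyses of PD-1 and PD-L1, pre-specified and taken one at a time.
2. For response and clinical benefit, use Fisher's exact test with an exact or Firth-penalised odds ratio.
3. For PFS and OS, use a permutation log-rank test or a Firth-penalised Cox model.
4. Give a 95% interval with every estimate.
5. Delete the time-dependent and extended Cox options for these analyses.
6. Either name one primary marker–endpoint pair, or state that all results are hypothesis-generating without multiplicity control.
7. Write *associated with outcome* in place of *predictive*.

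The cost is wording only: no added patients, visits or assays. Covariate-adjusted estimates are lost, which 20 patients cannot support. Exact tests are conservative (size below 3% here), and only very large effects can be detected, so the intervals should carry the message. Other exact or penalised methods would serve as well, if named in advance.

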The histopathology of BRCA-associated breast cancer suggests a role for the immune system in BRCA biology, based on several observations. Lymphocytic infiltrates are pathognomonic of medullary carcinoma of the breast, a subtype highly associated with BRCA 1 mutation, and lymphocytic infiltrates are commonly noted in BRCA-mutated cancers [8]. More recently the role of the immune system, tumor infiltrating lymphocytes (TILs), and the PD-1/PDL-1 pathway has been studied in breast cancer in general [9]. Of 116 breast cancers, 45% expressed PDL-1, with variation by molecular profile: 59% of triple negative, 33% of estrogen positive and 20% of HER2 positive breast cancers expressed PDL-1. TILs expressing PD-1 were also observed, with the highest proportion having concurrent expression of PD-1 TILs and PDL-1 tumor cells (45%) seen in triple negative breast cancer (TNBC). The only reported analysis of PDL-1 expression in BRCA mutated breast cancer to date indicated in a small subset of triple negative breast cancers, a significant correlation of PD-L1 and BRCA germline mutation, with 7 of 7 BRCA1 mutated breast cancers overexpressing PD-L1[10].

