Additional data regarding the expression of PDL-1 in BRCA-mutated cancers have been obtained through a study in collaboration with Merck and Cedars-Sinai Medical Center, for which [name] was the PI [11]. A cohort of 30 primary breast cancer tumor samples obtained prior to treatment from germline BRCA mutation carriers (identified previously by genetic testing) were identified within the Cedars-Sinai Pathology Department and were analyzed for relevant immune biomarkers through collaboration with Merck, The laboratory project, funded by Merck, assessed the expression of immune biomarkers PDL-1 and PD-1 using Merck-developed antibodies. The results of the study were as follows: Twenty (20) tumors were from BRCA 1 mutations carriers, and 10 were BRCA2, Sixteen (16) were basal type breast cancer (13 BRCA1, 3 BRCA2), 14 were estrogen receptor positive(ER+)(7 BRCA1, 7BRCA2), with 7 Luminal A and 7 Luminal B. There were no HER2 amplified tumors in the cohort. PD1 expression was observed in 11/30 (37%) of the cohort, and PDL1 expression was detected in 21/30 (70%) of the cohort. PDL1 expression was seen in 15/20 (75%) of tumors from BRCA1 mutation carriers, and 6/10 (60%) of tumors from BRCA2 carriers. PDL1 expression was present in 13/16 (81%) basal tumors and 8/14 (57%) ER+ tumors. Within the cohort of PDL1 expressing cancers. 7/21 (33%) were scored as "high" or "very high", 5 basal breast cancers and 2 ER+ cancers. The study therefore identified a high rate of PDL1 expression in untreated primary breast cancers with germline BRCA1 and BRCA2 mutations, regardless of intrinsic subtype. PDL-1 expression, in association with other relevant biomarkers, in BRCA-mutated cancers may predict a dependence

on immune suppression for tumor survival, and may predict responsiveness to immune checkpoint inhibition with pembrolizumab.

Evaluation of targeted therapy specific to the biology of BRCA-mutated cancers has been limited to the use of PARP inhibition, which acts through the mechanism of "synthetic lethality", inducing additional DNA damage and cytotoxicity in cells with homologous repair defects (HRD), and which produces a variety of dose-limiting toxicities, primarily hematologic.

Immunotherapy may offer a targeted therapy with less toxicity, and potentially greater efficacy for this population with an unmet need for targeted therapy approaches. Positive results in this cohort would be of major clinical research interest and benefit to this population.

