2.3 Exploratory and Correlative Objectives

2.3.1 Correlative Studies

The main objective of the translational research component of the IIT is to obtain biomarker measurements of PD-1 and PD-L1 expressions. Archival tumor samples will be sent to Qualtek Molecular Laboratories for analysis. See Sample Handling Manual.

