3.0 PATIENT ELIGIBILITY

3.1 Inclusion Criteria

- 3.1.1 Be willing and able to provide written informed consent/assent for the trial
- **3.1.2** Be ≥18 years of age on day of signing informed consent
- 3.1.3 Advanced BRCA-mutated and/or HDR-defect breast cancer progressing on or after prior therapy for metastatic disease or locally advanced disease; Prior therapy is defined as follows: for triple negative breast cancer progressing after at least 1 line of any prior chemotherapy; for HER2 positive disease must have progressed after at least two HER2 directed therapies in the metastatic setting including ado-trastuzumab emtansine (T-DM1); for hormone receptor positive disease (ER, PR, or both) must have progressed after a CDK4/CDK6 inhibitor plus hormonal therapy. Patients with progression within 12 months from previous neoadjuvant or adjuvant treatment could be enrolled in the study as 1st line therapy in metastatic setting.
- 3.1.4 Measurable disease by RECIST 1.1, with at least one lesion, not previously irradiated, that can be accurately measured at baseline as ≥ 10 mm in the longest diameter (except lymph nodes which must have short axis ≥ 15 mm) with computed tomography (CT) or magnetic resonance imaging (MRI) and which is suitable for accurate repeated measurements. Patients with non-measurable bone metastases in addition to measurable disease are eligible; however patients with non-measurable bone disease as the only site(s) of disease are not eligible.
- **3.1.5** ECOG 0 or 1
- **3.1.6** Documented BRCA deleterious germline or somatic mutation *AND/OR* HDR-defect.
- **3.1.7** FFPE tumor tissue available for analysis
- **3.1.8** Adequate organ function as defined in Table 1

Table 1 Adequate Organ Function Laboratory Values

System	Laboratory Value		
Hematological			
Absolute neutrophil count (ANC)	$\geq 1500/\mu L$		
Platelets	$\geq 100~000/\mu L$		
Hemoglobin	$\geq 10.0 \text{ g/dL or} \geq 5.6 \text{ mmol/L}^a$, with no blood		
	transfusion in the past 28 days		
Renal			
Creatinine OR	≤1.5 × ULN OR		
Measured or calculated ^b creatinine clearance	≥51 mL/min for participant with creatinine		
(GFR can also be used in place of creatinine or	levels >1.5 × institutional ULN		
CrCl)			
Hepatic			
Total bilirubin	≤1.5 ×ULN OR direct bilirubin ≤ULN for		
	participants with total bilirubin levels		
	>1.5 × ULN		

AST (SGOT) and ALT (SGPT)	≤2.5 × ULN (≤5 × ULN for participants with liver metastases)
Coagulation	

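### Section 9.3.5 grades associations between biomarkers on Cohen's kappa agreement bands, so for two different markers the grade depends on their prevalences and can understate the association

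*Combined protocol and SAP*

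**What the plan says.** Section 9.3.5 opens with its target: "Associations between biomarkers will be assessed using" Cohen's kappa, with 95% confidence intervals. It then gives the scale for reading the result: "Kappas of .75 or greater are considered excellent, whereas Kappas between .4 and .75 denote good agreement". Values below 0.4 get no label. The section does not name the biomarkers to be paired.

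Sections 2.3.1 and 8.0 describe the correlative work as obtaining "biomarker measurements of PD-1 and PD-L1 expressions" from archival tumour. No other biomarker is named there. Section 1.1 gives the only prevalences for both markers in BRCA-mutated tumours: "PD1 expression was observed in 11/30 (37%) of the cohort, and PDL1 expression was detected in 21/30 (70%) of the cohort".

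Other parts of Section 9.3 touch on relations between variables. Section 9.3.1 says "A scatter plot matrix will be used to explore the association among multiple variables". Section 9.3.2 relies on "careful initial assessment of correlations among all study covariates" to limit collinearity in its models. Section 9.3.3 lists chi-square, Fisher's exact test and logistic regression, for group differences and for modelling a binary response. None of these is assigned to describing a pair of biomarkers.

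**The concern.** Kappa measures whether two classifications put the same subject in the same category. That suits two readers or two assays of one marker. PD-1 and PD-L1 are not two readings of one thing: the cited study described in Section 1.1 reports PD-1 on tumour-infiltrating lymphocytes and PD-L1 on tumour cells. If one marker is simply more common than the other, kappa treats the excess as disagreement, however closely the two are linked.

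A grade from Section 9.3.5 therefore mixes three things: the strength of association, the prevalence of each marker, and the positivity cut-offs that set those prevalences. The same odds ratio can fall below *good* or well inside it. Measuring these two markers is the stated main aim of the translational component, so the risk is that a strong relation is reported as weak because the markers differ in frequency.

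**Working it through.** Section 9.3.5 states no numerical result to reproduce. The percentages it would act on do reproduce: 11/30 = 36.7% and 21/30 = 70.0%.

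**Inputs.** PD-1 prevalence a = 11/30 and PD-L1 prevalence b = 21/30 (Section 1.1); bands 0.40 and 0.75 (Section 9.3.5); n = 20 (Section 4.1). Section 1.1 gives no cross-table of the two markers, so the joint distributions below are assumptions.

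**Formulas.** Kappa = (po − pe)/(1 − pe), with pe = ab + (1 − a)(1 − b). For fixed prevalences the largest possible observed agreement is po = min(a, b) + min(1 − a, 1 − b), reached when one marker is fully nested in the other.

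**Step 1: ceiling at the Section 1.1 rates.**
- Nested table of 30: 11 both positive, 10 PD-L1 only, 0 PD-1 only, 9 both negative.
- po = 20/30 = 0.667.
- pe = (11 × 21 + 19 × 9)/900 = 402/900 = 0.447.
- Maximum kappa = (0.667 − 0.447)/(1 − 0.447) = 33/83 = **0.398**.
- On the same table phi is 0.498, the largest value these margins allow, and Fisher's p is 0.011.

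**Step 2: sensitivity of the ceiling to prevalence.** The exact 95% limits are 19.9% to 56.1% for 11/30 and 50.6% to 85.3% for 21/30.

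| PD-1 | PD-L1 | Maximum kappa |
|---|---|---|
| 19.9% | 70% | 0.19 |
| 56.1% | 70% | 0.71 |
| 36.7% | 50.6% | 0.72 |
| 36.7% | 85.3% | 0.18 |
| equal | equal | 1.00 |

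With PD-1 at 11/30 the ceiling is 0.40 or more for PD-L1 rates from about 12.6% to 69.8%. The narrow miss of 0.40 in Step 1 is therefore not the main point; the dependence on prevalence is.

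**Step 3: same association, different prevalences.** For a given odds ratio (OR), the both-positive share x solves x(1 − a − b + x) = OR·(a − x)(b − x), and then po = 1 − a − b + 2x. At OR 10 with a = 11/30 and b = 21/30, x = 0.3407, po = 0.6147 and kappa = (0.6147 − 0.4467)/0.5533 = 0.304.

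| OR | 11/30 and 21/30 | both 11/30 | both 50% | both 70% |
|---|---|---|---|---|
| 10 | 0.304 | 0.507 | 0.519 | 0.491 |
| 50 | 0.375 | 0.744 | 0.752 | 0.733 |

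An odds ratio of 50 earns *excellent* when both prevalences are 50% and no label at 37% and 70%.

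**Step 4: what 20 patients would show.** Take complete nesting as the truth, with cell probabilities 11/30, 10/30 and 9/30, and enumerate all samples of 20. Kappa reaches 0.40 in 46.4% of samples and 0.75 in 1.7%; the median is 0.375.

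**Step 5: a representative sample of 20.** With PD-1 in 7/20, PD-L1 in 14/20 and full nesting (7, 0, 7, 6), po = 0.65, pe = 0.44 and kappa = 0.21/0.56 = 0.375. Its asymptotic 95% interval is 0.08 to 0.67, which excludes zero. Fisher's p is 0.051, and the odds ratio is infinite with an exact lower limit of 0.77. PD-L1 positivity is 7/7 among PD-1 positive tumours (exact 95% CI 59% to 100%) and 7/13 among PD-1 negative tumours (25% to 81%).

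**The case against.** The strongest reply is that the bands grade agreement and say so. In the nested table of 30, ten tumours are discordant, so withholding a label of good agreement describes them correctly. On that reading the fault is one word, associations, in a passage otherwise about agreement. Concordant status is also a plausible question, since Section 1.1 cites co-expression of the two markers. This part stands: if concordance is meant, kappa can answer it. The text would still need correcting, because it states a different target.

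Second, the pair is inferred, and the Sample Handling Manual, not available here, might describe repeat reads of one marker. That cannot be excluded. The protocol itself, however, mentions no second reader or assay, and the plural target with only two named markers makes the inference reasonable.

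Third, the scatter plots and covariate correlations elsewhere in Section 9.3 would touch this pair. They would, but for exploration and collinearity. They promise no reported measure for the pair, and scatter plots say little about binary status.

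Fourth, the sizes are illustrative. Nesting and the odds ratios are hypothetical, and the 30 tumours were untreated primaries from germline carriers, whereas Section 3.1 admits "Documented BRCA deleterious germline or somatic mutation" and also HDR-defect disease. That limits any forecast for this trial, but not the finding that the grade moves with prevalence.

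Finally, nothing in the plan acts on a kappa grade, and the estimate and its interval will be reported whatever the label. That is why the point is minor.

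**Conclusion.** The concern holds as a low-severity point. Section 9.3.5 specifies an agreement statistic and agreement bands for a target it calls association, in a setting where the only named biomarkers are two different markers.

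The harm is an understated strength of association rather than a missed relation, and it is confined to an exploratory analysis. The size rests on three assumptions: that PD-1 and PD-L1 are the intended pair, that both are analysed as positive or negative, and that their prevalences in this trial differ roughly as they did in the earlier cohort. If the prevalences turn out equal, the ceiling disappears.

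**What to change.** Revise Section 9.3.5 to:

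- name PD-1 and PD-L1 as the pair and state the positivity cut-offs, or cite the Sample Handling Manual if it holds them;
- report the full 2x2 table and the percentage PD-L1 positive among PD-1 positive and among PD-1 negative tumours, each with an exact 95% CI;
- add an odds ratio with exact 95% CI and Fisher's exact test, and Spearman's correlation with 95% CI where scored expression is available;
- present these as estimates, since at n = 20 even a fully nested table may not reach conventional significance;
- drop the kappa bands as a grade of association. If kappa is kept, report it beside the 2x2 table and only as agreement: concordant status, or repeat reads of one marker.

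The cost is two to three sentences and no new data. The drawback is that the odds ratio may have no finite estimate in a small or nested table; the two percentages remain finite and carry the description. If a shorter edit is wanted, the table and the two percentages are the essential part.

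If concordance is what the authors intend, the alternative is to replace the word associations with agreement and still show the 2x2 table.
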